The following imputation of concurrent events in the preferred analysis of ICU duration, creating the most conservative assessment approach will be performed: a) for all death cases that have no recorded or known ICU hospitalization in this trial, start date will be imputed as date/time of death, end date will be imputed as Day 28 b) if ICU treatment is known and started before the date of death, start date will be the actual ICU submission, end date will be imputed as Day 28.

For patients who are lost to follow-up or discontinue the trial on or before Day 13 (last treatment day) due to any reason other than death and patients who discontinue with a last observed WHO clinical status no lower than that at Screening, the following approach will be performed: a) for cases that have no recorded or known ICU hospitalization in this trial, start date will be imputed as date/time of discontinuation, end date will be imputed as Day 28 b) if ICU treatment is known and started before the date of study discontinuation, start date will be imputed as actual ICU submission, end date will be imputed as Day 28.

As sensitivity analyses, ICU duration imputation on available data will be done as follows:

- for patients who died, the study period of 28 days will be recorded as ICU treatment duration,
- for patients who discontinued the study prematurely or for patients who died before EoS, the available information on ICU treatment duration until day of discontinuation will be used.

In Part 1, the ICU duration will be displayed with basic statistics per stratification factor age (< or \geq 65 years) and antiviral therapy (no antivirals, Hydroxychloroquine and Chloroquine, all other antivirals) and overall. In addition, an exact 2-sided 90% confidence interval for the median of differences between treatment groups (location shift) will be conducted adjusted for the stratification factors age and antiviral therapy.

28-day all-cause mortality

28-day all-cause mortality will be derived as percentage of patients who died due to any cause from time of 1st IMP administration until EoS. In Part 1, 28-day all-cause mortality will be displayed with frequency tables per stratification factor age (< or \geq 65 years) and antiviral therapy (no antivirals, Hydroxychloroquine and Chloroquine, all other antivirals) and overall. In addition, an OR with exact 2-sided 90% confidence interval will be conducted. The OR will be calculated adjusted for the stratification factors.

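### The two ICU-duration sensitivity rules both cover patients who died before end of study and give them different values; the second can score an early death as a short, favourable ICU stay.

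*Combined protocol and SAP*

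**What the plan says.** Duration of ICU treatment until Day 28 is a key secondary endpoint. For deaths, the preferred analysis in Section 16.3.2 extends the ICU period to Day 28. With no known ICU stay, "start date will be imputed as date/time of death, end date will be imputed as Day 28". With an ICU stay that began before death, "start date will be the actual ICU submission, end date will be imputed as Day 28". The stated aim is caution: "creating the most conservative assessment approach will be performed".

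The sensitivity rules follow under one lead-in: "As sensitivity analyses, ICU duration imputation on available data will be done as follows". There are two bullets:

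- Bullet 1: "for patients who died, the study period of 28 days will be recorded as ICU treatment duration".
- Bullet 2 names two groups together: "for patients who discontinued the study prematurely or for patients who died before EoS". Its instruction for both is that "the available information on ICU treatment duration until day of discontinuation will be used".

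The bullets carry no names, nothing marks them as alternatives, and neither is given priority. Section 16.3.1 separately names the set of patients surviving until EoS as a secondary or sensitivity set for the primary and key secondary endpoints, where applicable.

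**The concern.** A patient who dies before EoS falls under both bullets and receives two different durations. A programmer cannot tell whether to run one analysis or two.

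The more serious problem remains if the bullets are two analyses. Under bullet 2, death ends the ICU stay and nothing replaces the lost time. Since a shorter duration counts as better, a patient who dies soon after admission scores better than one who recovers after a longer stay. This runs against the direction chosen for the preferred analysis.

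A sensitivity analysis should show whether a result depends on the imputation. One that can improve as early mortality rises is hard to interpret, whether it agrees with the preferred analysis or not.

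**Working it through.** The plan states no figure that depends on these rules, so there is nothing to reproduce. The check applies the rules as written.

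**Inputs from Section 16.3.2.** Let A be the day of ICU admission and D the day of death. The one-minute term in the duration formula is ignored.

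- Preferred analysis: 28 − A if admitted to ICU before death; 28 − D if no ICU stay is known.
- Bullet 1: 28 for any death.
- Bullet 2: D − A if admitted. For a death without ICU I use 0. This is an assumption: the duration formula is written for patients transferred to ICU, and bullet 2 states no value for the others. Bullet 2 also stops the clock at the day of discontinuation, which is not defined for a death; I use the day of death.

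**Reading 1, one rule set.** Each death before EoS gets 28 from bullet 1 and D − A or 0 from bullet 2. These cannot both apply.

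**Reading 2, two analyses.** The contradiction goes. Bullet 1 is then silent on patients who discontinue for reasons other than death, and bullet 2 gives the last column below.

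| Patient | Preferred | Bullet 1 | Bullet 2 |
|---|---|---|---|
| Death Day 2, no ICU | 28 − 2 = 26 | 28 | 0 |
| ICU Day 3, death Day 5 | 28 − 3 = 25 | 28 | 5 − 3 = 2 |
| ICU Day 3, death Day 20 | 28 − 3 = 25 | 28 | 20 − 3 = 17 |
| Survivor, ICU Day 3 to 13 | 10 | 10 | 10 |
| Survivor, no ICU | 0 | 0 | 0 |

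Under bullet 2 the Day 2 death equals the best possible result, and the Day 5 death beats the survivor with 10 ICU days.

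**Illustrative arms.** All inputs here are assumptions: 100 patients per arm, 30 per arm in ICU, ICU survivors staying 10 days, and every death on Day 5 after admission on Day 3. Take 10 deaths on IMU-838 and 5 on placebo.

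- Preferred: (10 × 25 + 20 × 10)/100 = 4.50 against (5 × 25 + 25 × 10)/100 = 3.75.
- Bullet 1: (10 × 28 + 20 × 10)/100 = 4.80 against (5 × 28 + 25 × 10)/100 = 3.90.
- Bullet 2: (10 × 2 + 20 × 10)/100 = 2.20 against (5 × 2 + 25 × 10)/100 = 2.60.

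The mean under bullet 2 favours the arm with twice the deaths. With 16 against 5 deaths, the means are 5.40 against 3.75, 5.88 against 3.90, and 1.72 against 2.60. The medians among ICU patients are 25 against 10, 28 against 10, and 2 against 10. With 10 against 5 deaths, the medians among ICU patients are 10 in both arms under every rule.

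**What does not move.** In these arms 70 of 100 patients have 0 days, so the all-patient median is 0 under every rule. For the unadjusted location shift there are 100 × 100 = 10,000 between-arm pairs. Of these, 30 × 70 = 2,100 are positive, 70 × 30 = 2,100 are negative, 70 × 70 = 4,900 are zero, and 30 × 30 = 900 compare two ICU patients. At most 2,100 + 900 = 3,000 pairs lie on either side of zero, fewer than half, so the median difference is 0 under every rule. The plan's estimate is also adjusted for strata, which this check leaves out.

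**The case against.** The strongest defence is that the plural wording announces two analyses. Bullet 1 is then harsher on deaths than the preferred rule and bullet 2 is the observed-data version, so together they bracket it. If bullet 1 changes only the handling of deaths, the preferred rule can be taken to stand for everyone else. Section 16.3.2 also plans analyses on available information for the primary endpoint and for survival without respiratory failure, so bullet 2 fits a pattern. Mortality is reported as its own key secondary endpoint, so a reversal in ICU duration would be read beside it.

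Much of this stands. The two-analysis reading is plausible and removes the contradiction, so a flat charge of self-contradiction would go further than the text supports. The default for other patients is reasonable, though unstated. The bracketing is also real. What does not follow is that the lower bound is useful: it is low because death shortens the stay, so it mixes a change of imputation with a reward for early death.

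A reader might also infer that the gap between the bullets is large enough to threaten the criterion in Section 16.4.2 of a median ICU stay about 1.5 days shorter. The documents do not support that. The criterion is a between-arm difference in medians, whereas the gap between the bullets is a difference between two rules in one arm's mean. Section 16.4.2 does not tie the criterion to these sensitivity analyses, and the all-patient median need not move at all.

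**Conclusion.** The point holds in a limited form. The two bullets overlap for every death before EoS and are neither labelled nor ranked. On the more favourable reading, bullet 1 leaves other discontinuations unstated, and bullet 2 can favour the arm with more early deaths.

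Per patient, an early ICU death can score 2 instead of 25 or 28 days, and a Day 2 death without ICU can score 0 instead of 26 or 28. The 0 rests on counting no ICU stay as zero. The size and direction of any between-arm effect depend on how many early deaths each arm has and how soon after admission they occur. The documents do not give this, so the two-arm figures show only that a reversal can happen.

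A reader might infer that the main ICU-duration result is biased. It is not biased by this defect: the preferred analysis carries deaths to Day 28 and does not treat an early death as a short stay. The problem lies in sensitivity analyses of one key secondary endpoint, in a Part 1 that is descriptive and has no formal tests. It is worth correcting because a stated rule can mislead and the correction is easy.

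**What to change.** In the second bullet of Section 16.3.2, delete the words that add patients who died before EoS. The two bullets then form one sensitivity analysis: deaths count as 28 days, and patients who discontinue for other reasons contribute their observed ICU time.

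If an analysis of observed days alone is still wanted, give it its own label, restrict it to the surviving-patient set already named in Section 16.3.1, and report it beside 28-day mortality because it conditions on survival.

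The cost is one phrase in the protocol and matching text in the SAP, which Section 16.3.1 says will be finalized before the data are analyzed. No new data, visits or patients are needed. The small downside is the loss of the observed-data bound for patients who died.

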5.1 Background COVID-19

The World Health Organization (WHO) declared severe acute respiratory syndrome coronavirus 2 (SARS-CoV-2) infection (causing coronavirus disease 2019, COVID-19) a pandemic on March 11, 2020. [3] Main clinical symptoms include fever, cough, myalgia or fatigue, expectoration, and dyspnea. [4] While most patients do not experience severe symptoms, one meta-analysis found that approximately 18% of cases were severe. [5] Fatality rates are estimated to be approximately 4-7% at this time. [4,5]

Figure 2: Classification of COVID-19: disease states and potential therapeutic targets

Taken from [6].

Two distinct but overlapping pathological pathways appear to be involved in the course of the disease. The first is triggered by the virus itself and the second comprises the host response.

A 3-stage classification of the disease was proposed by Siddigi and Mehra. [6] The initial stage occurs at the time of inoculation and early establishment of the disease. For most people, this involves an incubation period associated with mild and often non-specific symptoms such as malaise, fever and a dry cough. Treatment at this stage is primarily targeted towards symptomatic relief. Should a viable antiviral therapy be proven beneficial, targeting selected patients during this stage may reduce duration of symptoms, minimize contagiousness and prevent progression of severity.

In the second stage of established pulmonary disease, viral multiplication and localized inflammation in the lung is the norm. During this stage, patients develop an interstitial lung disease (viral pneumonia), with cough, fever and possibly hypoxia. Treatment would primarily consist of supportive measures and available antiviral therapies. If hypoxia ensues (Stage IIb), it is likely that patients will progress to requiring mechanical ventilation and, in that situation, the use of anti-inflammatory therapy may be useful.

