16.1 Sample size calculation

Part 1

As no formal hypothesis testing will be conducted in Part 1, no formal sample size calculation is deemed necessary. In previous protocol versions, a pooling of p-values of Part 1 and Part 2 was planned and a sample size of N = 200 enrolled patients (100 per group) was calculated. It is assumed that with the previously planned sample size a robust estimation of all efficacy and safety parameters can be conducted. Thus, no adaptations in sample size for Part 1 are necessary.

Previously, the following assumptions were made:

3-stage group sequential adaptive test design with O'Brien and Fleming shaped boundaries

Information rate for Part 1 analysis: 0.2

O'Brien and Fleming alpha level for end of Phase 2 analysis: <0.0001

Primary endpoint: Proportion of patients without any need for invasive ventilation

Randomization ratio: 1:1 (45 mg/day IMU-838:placebo)

Power: 80%

Global significance level: 0.05, 1-sided

Proportions of patients with need for INV

for 45 mg/day IMU-838:	32%
for placebo:	40%
Number of patients (Part 1):	188

Considering a 6% drop-out rate, a total of 200 patients (100 per group) were to be enrolled.

Part 2

If the trial is expanded to Part 2, the sample size of Part 2 will be determined based on the results of MA1.

The Part 2 (Phase 3, Expansion Phase) trial will be designed to keep a global 1-sided alpha level of 0.025 (one-sided). A 2-stage group sequential test adaptive design with O'Brien and Fleming shaped boundaries will be used. Stage 1 will be IA2 applying an overall information rate of 50% and using an alpha of 0.0026. The use of group sequential boundaries within the context of an adaptive design is enabled using the inverse normal method, combining the p-values of both stages with weights based on the sample sizes. Statistical analysis methods that control for the Type I error will be used.

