Patients who discontinued the trial before Day 28 due to any other reason than death will be considered as deaths, unless survival status can be obtained by the investigator through other means (see Section [12.4](#)).

In a sensitivity analysis, patients who discontinued before EoS due to reasons other than death, will be considered as survived, unless the investigator has any information of patient death after discontinuation.

In Part 2, the primary endpoint (as selected during MA1) and the key secondary endpoints that include proportion of patients (e.g. patients without respiratory failure, 28-day all-cause mortality) will be evaluated for superiority of IMU-838 vs placebo with an exact Cochran-Mantel-Haenszel test, adjusted for the stratification factors age and antiviral therapy. In addition, logistic regression analyses will be conducted including the covariates age, antiviral therapy, sex, and country. The distribution of primary endpoint or any key secondary endpoint containing duration measurements (e.g. duration of ICU treatment) will be analyzed with the van Elteren test (stratified by age and antiviral therapy). In addition, time-to-event analyses using Kaplan Meier methodology and a stratified log rank test (stratification factors age and antiviral therapy) will also be performed. All tests will be performed 1-sided keeping a global alpha level of 0.025 (1-sided).

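### The main 28-day mortality analysis counts every discontinued patient of unknown survival status as a death, so a key secondary estimate mixes death with drop-out and can err in either direction.

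*Combined protocol and SAP*

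**What the plan says.** Section 16.3.2 of the protocol defines the endpoint by actual deaths: "28-day all-cause mortality will be derived as percentage of patients who died due to any cause". The main-analysis rule that follows is wider: "Patients who discontinued the trial before Day 28 due to any other reason than death will be considered as deaths", except where their survival status is established some other way. A sensitivity analysis makes the opposite assumption. There, patients who discontinue for reasons other than death "will be considered as survived, unless the investigator has any information of patient death after discontinuation".

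Sections 8.1 and 12.5 and the notes to Table 3 provide for tracing survival status through the patient, relatives, the referring physician, registers or public information. Section 17.2 limits this. After withdrawal of consent no more data are to be sought, unless the patient allows non-interventional follow-up. Transfer to an institution that the investigator cannot reach counts as loss to follow-up.

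In Part 1 the endpoint gets an odds ratio with an exact 90% confidence interval, adjusted for age and antiviral therapy, and no formal test. Section 16.4.2 uses a relative reduction in deaths of 8% or more as one leg of the activity rule. It does not say which version of the mortality result applies there.

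The documents state no expected mortality for this trial. Section 5.1 gives only general background: "Fatality rates are estimated to be approximately 4-7% at this time". Section 16.1, reporting the assumptions of previous protocol versions, says: "Considering a 6% drop-out rate, a total of 200 patients (100 per group) were to be enrolled". No rate of unknown survival status is given.

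**The concern.** The rule turns patients who are not known to have died into events of an endpoint defined by death. If true mortality is of the same order as the proportion of unknown status, the estimate reflects retention as much as survival.

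Two consequences follow. Adding about the same number of imputed deaths to both arms dilutes a real effect. Adding different numbers moves the estimate towards whichever arm keeps its patients better, whatever the drug does to mortality. Because Part 1 has no tests, point estimates drive the decision to open Phase 3. Section 16.3.2 also lists 28-day mortality among the Part 2 confirmatory endpoints, subject to amendment, so the rule could carry over.

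**Working it through.** **Inputs.** Sample size: 188 patients, 6% drop-out, 200 enrolled at 100 per arm (Section 16.1). Mortality m: 4-7%, midpoint 5.5% (Section 5.1, background only, so an assumption here). Unknown status after tracing u: not stated. I take 6% (no drop-out traced) down to 1.5% (three quarters traced).

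**The plan's own figure.** 188 / (1 - 0.06) = 200, as stated. So 6% of 200 is 12 patients.

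**Share of counted deaths that are imputed.** Share = u / [u + (1 - u)m], where all patients of unknown status are counted as dead.

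| Unknown u | Imputed deaths | Real deaths among the rest, m = 4% / 7% | Share imputed, m = 4% / 7% |
|---|---|---|---|
| 6% | 12 | 7.5 / 13.2 | 61% / 48% |
| 3% | 6 | 7.8 / 13.6 | 44% / 31% |
| 1.5% | 3 | 7.9 / 13.8 | 28% / 18% |

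The share reaches one half at u = m / (1 + m). That is 3.8% for m = 4% and 5.2% for m = 5.5%, or about 64% and 87% of a 6% drop-out left untraced. For m = 7% it is 6.5%, which is not reached even with no tracing.

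**Dilution when unknown status is balanced.** Apparent ratio = [u + (1 - u)m × RR] / [u + (1 - u)m]. For m = 5.5% and true RR = 0.50:

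- u = 2%: 0.04695 / 0.0739 = 0.64
- u = 4%: 0.0664 / 0.0928 = 0.72
- u = 6%: 0.08585 / 0.1117 = 0.77

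Reported mortality in the control arm is then 7.4%, 9.3% and 11.2%, against a true 5.5%.

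**Effect on the 8% leg, balanced case.** The true relative reduction needed to display 8% is 0.08 × [u + (1 - u)m] / [(1 - u)m]. At u = 6% this is 21% (m = 4%) or 15% (m = 7%). At u = 1.5% it is 11% or 10%.

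**Unbalanced case.** 100 per arm, m = 7%, 12 patients of unknown status in total:

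| True RR | Unknown, IMU-838 / placebo | Counted deaths | Apparent RR |
|---|---|---|---|
| 1.00 | 4 / 8 | 10.72 / 14.44 | 0.74 |
| 1.00 | 8 / 4 | 14.44 / 10.72 | 1.35 |
| 0.80 | 4 / 8 | 9.38 / 14.44 | 0.65 |
| 0.80 | 8 / 4 | 13.15 / 10.72 | 1.23 |

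The rows show, in order, a benefit created, a harm created, a benefit exaggerated and a benefit reversed.

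For comparison, take the first row (no true effect, 4 / 8). Counting only known deaths gives 96 × 0.07 = 6.72 against 92 × 0.07 = 6.44, a ratio of 1.04. With deaths rare, the known-death count is far less sensitive to who drops out.

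**The case against.** The plan has real safeguards. The imputation applies only after tracing fails, and the tracing provisions are broad. The opposite imputation is pre-specified, so the two results already bracket the answer. Time to death is a separate endpoint and is on the activity list. Part 1 is descriptive, and the Part 2 analyses may change by amendment. Worst-case imputation also matches the approach that Section 16.3.2 calls conservative for ICU duration.

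The 8% leg is fragile with or without imputation. At 5.5 real deaths per 100, one fewer real death is an 18% reduction (1 / 5.5). At 11.2 counted deaths, one fewer is 9% (1 / 11.2). Nor does the leg act alone: it needs at least a 10% relative effect on the primary endpoint and a consistent overall pattern. Kaplan-Meier has its own weakness if patients who leave differ in risk from those who stay.

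Much of this stands, and it limits two stronger readings that a reader might infer. One is that about half of all reported deaths would be imputed. That needs most or all of a 6% drop-out to stay untraced. The 6% is a drop-out assumption from a superseded calculation, not a rate of unknown survival. The 4-7% is a general background rate, while the trial enrols hospitalised patients, with 32-40% assumed to need invasive ventilation. If mortality were 10-15% (an assumption), the share would be 39-30% even with no tracing. The other is that an effect is always pulled towards none. That is assured only when unknown status is about equal between arms.

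The safeguards do not remove the problem. Tracing is closed for patients who withdraw consent without agreeing to follow-up. The sensitivity analysis shows how far the result depends on imputation, but the main estimate remains the imputed one and Section 16.4.2 does not say which to use.

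**Conclusion.** The point holds. Followed exactly, the rule gives a main mortality estimate that mixes death with drop-out, contrary to the endpoint's own definition. Under the assumed 4-7% mortality and 1.5-6% unknown status, 18-61% of counted deaths would be imputed. The upper part of that range requires poor tracing together with low mortality, and the share falls if mortality is higher. A true ratio of 0.50 would appear as about 0.64-0.77 at 5.5% mortality and 2-6% balanced unknown status. With unbalanced unknown status the estimate can move either way, so the rule cannot be defended as conservative.

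The documents do not support saying that half the deaths will be imputed, that the bias has a fixed direction, or that the mortality leg alone could open Part 2. The change is worth making because this is a key secondary endpoint and an input to the go/no-go decision.

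**What to change.** In Section 16.3.2 and the SAP:

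- Base the main mortality analysis on known deaths. Use the Kaplan-Meier 28-day death proportion by arm, censoring at the last date known alive, including status found by tracing. Keep age and antiviral therapy as strata in the treatment comparison.
- Keep drop-out counted as death and drop-out counted as survived as the two bounding sensitivity analyses. The planned stratified odds ratio with its exact 90% interval can be reported for both.
- Tabulate by arm the observed deaths and the patients of unknown status.
- State in Section 16.4.2 that the 8% criterion uses the main, known-death estimate.
- Correct the cross-reference. The rule points to Section 12.4 (unscheduled visits), but the tracing text is in Section 12.5.

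The cost is protocol and SAP wording, plus specifying and programming a stratified Kaplan-Meier comparison in place of the odds ratio as the main result. Death timing is already needed for the time-to-death endpoint, but the last date known alive must be recorded for every traced patient. The downside is reliance on non-informative censoring, which the two bounds test. The change does not cure the fragility of an 8% threshold when deaths are few.
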